Approach to Missing Data

Our initial analyses will only use observed data. When data are missing for items within scales, we will use recommended imputation procedures rather than excluding participants from the analyses. For missing follow-up assessments, we will check if missingness is associated with any baseline variables including sites, and will include any such baseline variables in the models evaluating the intervention effect described above. In addition, as described under Effect Over time, the mixed-effects model is expected to provide an unbiased estimate of the intervention effect if missingness is at random. As a secondary analysis, we will also conduct an analysis that imputes missing data. We will likely have some missing baseline values in addition to missing follow-up assessments. Thus we will conduct multiple imputations based on chained equations (sequential regression multivariate imputation) to impute both baseline and follow-up data and will summarize the data using appropriate combination rules. (107, 108)

REGULATORY, ETHICAL AND STUDY OVERSIGHT CONSIDERATIONS

Informed Consent Process

Patients who appear to meet study inclusion and exclusion criteria based on review of medical records and consultation with the attending psychiatrist will be approached by the research assistant (RA) to describe the study, provide information about the randomization and 3 and 6-month assessments, as well as the risks, benefits, and limitations to confidentiality. Patients who state they are interested will be asked to complete a brief cognitive screener to assess whether they are substantially cognitively impaired and therefore unable to give informed consent. Patients who are not substantially cognitively impaired will complete a pre-screening consent form allowing study staff to administer the Beck Suicide Scale and items 4 and 5 of the Columbia Suicide Scale. Patients who have a score >5 on the Beck Suicide Scale will be eligible to participate and obtain informed consent. During the informed consent process, the study will be described and patients will have ample and repeated opportunities to ask questions.

We are requesting a waiver of consent for recruitment purposes. We will be screening medical records to determine patient eligibility. Due to the large number of patients admitted to the inpatient psychiatric unit, it would be difficult to obtain consent from each patient prior to screening. The risk to patients is minimal in order to allow staff to pre-screen medical records. Patients who are interested in participating will provide informed consent before study activities begin.

Telephonic Informed Consent Procedures During COVID-19 Pandemic: Subjects who enroll over the telephone due to COVID-19 restrictions will be provided with paper copies of consent forms for their records, and consent will be obtained verbally over the phone after reviewing the consent documents in detail and providing the patient ample opportunity to ask questions. Research staff will allow patients as much time as they wish to review the consent documents, and then they will read an informed consent script to the patient. Research staff will pause frequently and check in with the patient, asking if they understand what is being asked of them, and if they have any questions. For each signature line in the consent forms, research staff will ask the patient to provide verbal consent. Once consent is obtained, research staff will document the date that the subject consented in the study's de-identified database.

Confidentiality and Privacy

Every effort will be made to ensure that study data are always confidential, and never stored so that data can be linked to a particular person. Confidentiality will be explained to participants, including assurances that law enforcement personnel, and any others outside the research staff will not be informed of their responses. Limits to confidentiality will be explained verbally and in writing (e.g., physical or sexual abuse of minors, imminent threat to harm self or others).

Future Use of Stored Data

Data will be retained for study recordkeeping purposes until the end of analysis period and at least seven years from the end of the study period, in keeping with the relevant record-keeping guideline. There will not be any change in the conditions or arrangements for storage of research data/specimens during the retention period.

Data Handling & Recordkeeping

Data collection is the responsibility of the clinical trial staff at the site under the supervision of the site investigator. The investigator is responsible for ensuring the accuracy, completeness, legibility, and timeliness of the data reported.

All source documents should be completed in a neat, legible manner to ensure accurate interpretation of data.

Preliminary eligibility data will be collected from participant's electronic medical records and entered into a 21 CFR Part 11-compliant Microsoft Access database provided by the University of Michigan. This data will also be stored in a Box folder approved for use with sensitive data by the University of Michigan. Any data that contains direct identifiers will be stored separately from deidentified data. Data backups will be performed regularly. This data will be linked by a coded identifier to direct identifiers (name, phone number, address, and medical record number) but stored separately. Data need to be linked to subjects' identities to help facilitate follow-up data collection procedures. Identifiers will be retained in accordance with the requirements of record-keeping for regulatory purposes.

Clinical data will be entered directly from the electronic medical record.

Outcome assessment data will be collected at baseline, 3 months, and 6 months using Qualtrics, an Application Server Provider (ASP) with a Software-as-a-Service (SaaS) platform for the creation and distribution of online surveys and related services. The platform records response data, and performs analysis and reporting. All services are located online. Qualtrics servers are protected by high-end firewall systems, and vulnerability scans are performed regularly. Complete penetration tests are performed yearly. All have quick fail over points with redundant hardware, and complete backups are performed nightly.

Qualtrics uses Transport Layer Security (TLS) encryption, known as SSLv3.1, for all Internet transmitted data. Surveys may be protected with passwords. Qualtrics services are hosted by trusted third party data centers that are SSAE-16 SOC 1 Type II audited. All data at rest are encrypted, and data on deprecated hard drives are destroyed by U.S. DOD methods and delivered to third-party data destruction service.

Outcome assessments may be collected using paper surveys if internet access is unavailable during the time of the assessment, or based on a participant's needs or preferences. Paper copies of outcome assessment data will be linked to direct identifiers using a coded identifier. Deidentified data will always be stored separately from identifiable data. All paper records will be stored behind lock and key in locations that are only accessible to study staff who have been granted permission to use the data.

If outcome assessments are conducted off-site, paper copies of outcome assessment data may be transported by study staff from the location of the outcome assessment to the secure storage site. Data will be transported directly back to the storage site by study staff, and will remain on our person at all times.

Peer research assistants will transport any handwritten clinical notes in a combination lockbox. These handwritten notes will be de-identified. Handwritten notes will be linked to direct identifiers using a coded identifier, and will stored separately from identifiable data behind lock and key in locations that are only accessible to study staff who have been granted permission to use the data.

Peer research assistants may choose to keep electronic clinical notes using a Box folder that has been approved for storage of sensitive data by the University of Michigan. Electronic notes will be de-identified and linked to direct identifiers using a coded identifier.

Per the Informed Consent protocol, research staff will collect a Suicide Safety Plan from participants assigned to the Peer Mentorship intervention upon discharge from the inpatient unit. These safety plans will be stored electronically in a Box folder approved by the University of Michigan for storage of sensitive data. Safety Plans contact direct identifiers and will therefore be stored separately from deidentified data.

Quality Assurance and Quality Control

[name] will directly supervise the data manager and the project coordinator and will be responsible for monitoring confidentiality procedures. Quality control and reliability of screening, baseline and follow-up assessments will be monitored by [name] throughout the trial via regular meetings and observation of the project coordinator conducting standardized assessments. [name], the study biostatistician, will monitor the quality of the data files via supervision of the data manager.

Training

[name] will ensure that all relevant IRB policies, procedures and stipulations are being followed. [name] also will be responsible for ensuring that other investigators and project staff adhere to the UM IRB policies including: (1) all participants will understand, agree to and sign a written consent form before participating; (2) strict adherence to a participant's right to withdraw or refuse to answer questions will be maintained; (3) the assessments will be completely confidential and no names will be associated with the assessment data; (4) consent forms and identifying information will be kept separate from the actual participant data; (5) all identifying information (consents, tracking data) will be kept locked at all times and computer files will be saved with passwords; (6) participants will be informed in writing in the consent form how to contact the PI, the study coordinator, and UM IRB office with any questions and/or concerns.

[name] in cooperation with Co-Investigators will be responsible for providing training to all research staff working with participants with regard to procedures for managing potential clinical deterioration, suicidal crisis situations, and/or adverse events. This training will include information regarding evaluating warning signs of acute suicidal ideation, planning, or intent that could occur during contact with participants, and means of addressing such issues. Peer mentors will inquire about suicidal ideation at every encounter with participants, and participants complete self-report measures of suicidal ideation at baseline, 3-month, and 6-month assessments conducted by RAs. In the case that a participant indicates any level of suicidal ideation or recent attempt during encounters with any study staff (including peer mentors), a suicide risk management protocol will be used. The protocol utilizes an algorithm of scripted risk assessment questions and “action steps” dependent on the participant responses. Based on the level of risk determined by the algorithm, study staff may perform one or more of the following: a) recommend the participant call or be transferred to the national suicide crisis hotline, the University of Michigan’s Psychiatric Emergency Services (PES), or the nearest emergency department to immediately address suicide risk and determine whether emergency medical services or police should be activated to conduct a wellness check in the patient’s home or community, b) notify the participant’s outpatient treatment providers regarding a non-imminent increase in suicide risk, c) notify a designated on-call study team clinician ([name], [name], or [name],) when the suicide risk management algorithm has been activated, and when any questions arise regarding risk management. The on-call study clinician will be available via pager or cell phone at all times when there is potential contact between study staff (including peer mentors) and participants.

Participants will be instructed on how to contact the national suicide crisis hotline, PES, or closest emergency department if they are experiencing a suicidal crisis. Peer mentors and study team members are not to further assess or manage suicide risk beyond the established protocol. In order to avoid participants contacting peer mentors in crisis when study clinicians are not available, peer specialists will be provided with cellular phones specifically for communication with study participants, and participants will be clearly informed that these cell phones will be off when not in use, and they are not monitored at all times. The voicemail messages on these phones will have instructions on how to contact crisis services. When Peer mentors will meet with participants outside of regular business hours; clinician back up will be prearranged. Written safety procedures for conducting community-based meetings include use of public locations, during daylight hours, and mandatory call-in procedures. In our prior research, using such procedures with similar populations, no incidents where staff safety concerns became an issue occurred during follow-up assessments. All safety concerns will be reported immediately to [name].

Protocol Deviations

A protocol deviation is any noncompliance with the clinical trial protocol, International Conference on Harmonisation Good Clinical Practice (ICH GCP), or Manual of Procedures (MOP) requirements. The noncompliance may be either on the part of the participant, the investigator, or the study site staff. As a result of deviations, corrective actions are to be developed by the site and implemented promptly.

It is the responsibility of the site investigator to use continuous vigilance to identify and report major protocol deviations that may adversely impact safety of participants, or impact integrity/validity of the data, and minor protocol deviations as part of a pattern or suggesting a systemic problem in study conduct that potentially places subjects or others at a greater risk of harm than was previously known or recognized, within seven (7) calendar days of becoming aware of the event or information.

Monitoring

The Principal Investigator, [name], will be responsible for monitoring the data safety and quality. It should be noted that all research projects involving human participants at the University of Michigan, including the proposed, require approvals from the University of Michigan Medical School’s Institutional Review Board (IRBMED). In addition, because of the sensitive nature of the data being collected, a Certificate of Confidentiality will be requested.

[name] will ensure that all relevant IRBMED policies, procedures, and stipulations are being followed. They will also will be responsible for ensuring that other investigators and project staff adhere to the UM IRBMED policies including: (1) All participants will understand, agree to and sign a written consent form before participating; (2) strict adherence to a participant’s right to withdraw or refuse to answer questions will be maintained; (3) study assessments will be confidential and no names will be associated with the assessment data; (4) consent forms and identifying information will be kept separate from the actual participant data; (5) all identifying information (consents, tracking data) will be kept locked in a filing cabinet at all times and computer files will be saved with passwords; and (6) participants will be informed, in the consent form, how to contact the PI, the study coordinator, and the IRBMED office with any questions and/or concerns. [name] will be

responsible for reporting any amendments to the UM IRBMED prior to implementation of any changes to the protocol.

[name] in cooperation with Co-Investigators will be responsible for providing training to all research staff working with participants with regard to procedures for managing potential clinical deterioration, suicidal crisis situations, and/or adverse events. This training will include information regarding evaluating warning signs of acute suicidal ideation, planning, or intent that could occur during contact with participants, and means of addressing such issues. All safety concerns will be reported immediately to [name].

An independent Data Safety Monitoring Board will be established that will review: (a) research protocols and plans for data and safety monitoring, (b) adverse events and unforeseen outcomes, (c) ethical issues related to recruitment activities, (d) risk management policies and activities, and (e) conduct intermediary data analyses, when appropriate. The board will be approved by the PIs, sponsoring Institute, and the University of Michigan Medical School IRB. DSMB members will be responsible for defining the events that will trigger additional “as needed” reviews and the criteria for retaining or removing patients from studies if they suffer from an adverse event. In addition, the DSMB will make recommendations to the study investigators about continuation or discontinuation of the project. These responsibilities are in line with the “NIH Policy for Data and Safety Monitoring” and further Guidance on Data and Safety Monitoring for Phase I and Phase II Trials.” The DSMB members include scientists and clinicians with expertise in randomized controlled trials, psychiatric emergencies, and statistical analysis. The DSMB will meet in year 1 prior to the enrollment of the first participant and then every 6 months until the trial concludes, and will be informed promptly of all serious adverse events. The DSMB will meet “as-needed” to discuss new study protocols and adverse events occurring between scheduled meetings.

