Although peer support services began historically as an alternative to psychiatric treatment, there has been increasing integration of peer services into mental health treatment with the advent of professionalized, certified peer specialists. (5, 53) Peer specialists are individuals with a lived experience of mental illness who receive formal training, certification, and employment in providing peer support. PREVAIL was designed to be delivered by peer specialists in part because they are already integrated with many community mental health programs and provide a wide range of recovery-oriented, patient-centered services. (54) The State of Michigan has trained and certified 1,640 peer specialists, and an estimated 24,000 have been certified nationwide. (12) In 2014, 34 states also offered Medicaid reimbursement for peer support services, furthering sustainability of these services. (55) The State of Michigan also trains peer recovery coaches, individuals who have lived experience receiving public mental health services specific to substance use, and who serve similar populations in community mental health programs; Michigan offers reimbursements for peer recovery coach services through public substance abuse treatment funds. With the integration of peer providers into mental health treatment services, programs are increasingly involving peers in crisis services. (56-58) However, peer specialist certification training and peer recovery coach training does not currently address suicide or how peers might be most useful to individuals with suicidal ideation or behaviors. Thus, there is likely substantial demand for an effective protocol for peer providers who are supporting high-risk individuals.

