Intervention development and peer mentor training. During the intervention development phase of the R34 project, an expert panel including suicide prevention researchers ([name], [name], [name]), peer support researchers ([name], [name]), peer specialists ([name], [name]), the peer support training director for the State of Michigan ([name]), and an inpatient psychiatry unit director ([name]) were convened to create an outline of the essential training needs for peer mentors to work with high-risk patients and address suicide risk according to the interpersonal theory of suicide. The outline of the training and intervention content was then used as the basis for developing the training manual (Other Attachment IIA). This manual was developed by the PI ([name]) in conjunction with [name] and [name] of the Center for Dignity, Recovery, and Empowerment (a peer support advocacy, service, and research organization); [name], a clinical psychologist with expertise in peer support; and [name], a clinical psychologist and post-doctoral fellow. Drafts of the training materials were circulated among the expert panel and revised in an iterative process.

The training was then delivered over 3 days to the study's 4 peer mentors utilizing adult learning theory with small group discussions, role plays, and video vignettes. (The term "peer mentor" indicates a peer specialist or peer recovery coach with PREVAIL training.)

Acceptability and feasibility. A "pre-pilot" in which each peer mentor delivered the intervention to 1 or 2 participants was conducted; the only significant change to the study protocol was to allow mobile device and social media communication with participants. The pilot RCT phase of the study was launched and successfully enrolled 70 participants (Figure 3). 375 patients with medical record documentation of suicidal ideation or suicide attempt at admission were screened, 225 of whom were not eligible and 80 of whom refused participation. The most frequent reasons for ineligibility were unstable psychosis, cognitive disorder, or severe personality disorder as determined by

Figure 3. Consort Diagram for PREVAIL Pilot Study

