Patients will be excluded if they are: 1) substantially cognitively impaired (according to the Mini-Cog(78, 79); for patients unable to read an analog clock, the Mini Mental State Exam will be administered instead, and for patients who are screened via telephone, the Callahan Six-Item Cognitive Screener (119) will be used), 2) unable to provide informed consent for any reason (including incompetency), 3) determined by the patient's attending psychiatrist that peer mentorship is not appropriate due to unstable psychosis, cognitive disorder, or severe personality disorder, 4) already receiving or intending to receive individual peer mentorship from a Certified Peer Support Specialist, or group-based peer support with a focus on suicide prevention, on a biweekly or more frequent basis, 5) residing outside of the state of Michigan, 6) planning to be discharged to another inpatient or residential facility, 7) receiving electroconvulsive therapy (which prolongs the hospital stay and complicates informed consent and peer interactions due to risks of memory impairment), or 8) have a legal guardian, meaning that the patient is not able to provide informed consent to participate.

Recruitment

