15. Medication adherence, as measured by the Single-Item Self Rating (SISR) Scale for Medication Adherence
16. Change in perceived meaning in life, as measured by the Meaning in Life Questionnaire (MLQ), a 10-item measure of the presence of and search for meaning in life (115).

STUDY INTERVENTIONS

Delivery and Duration

The peer mentorship intervention will be delivered by peer providers – peers specialists or peer recovery coaches - trained and certified by the State of Michigan. Michigan is a leader in the training and deployment of peer specialists with over 1,600 peer specialists currently trained. The State training for peer specialists consists of 24 hours of didactic and group-based learning sessions covering role definitions and boundaries, effective communication, combating negative self-talk, problem solving, and supporting recovery through the use of the peer specialist's own recovery story and other recovery dialogues, while the training for peer recovery coaches focuses on multiple pathways to recovery and motivational interviewing. Peer specialists and peer recovery coaches are offered the same continuing education programs provided by the state, and both types of peer providers utilize their lived experience with recovery to support others. The study will hire certified peer providers with at least one year of professional experience providing peer support to individuals with mental health conditions. Peer specialists will also be required to be in stable recovery (i.e., continuous employment with no psychiatric hospitalization in the past year) and must be capable of speaking to a lived experience with suicidal thoughts or behaviors.

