Peer providers will be hired for the study from the pool of those already trained in the intervention during the R34, and new peer providers will be recruited with the assistance of the director of peer specialist training in the State of Michigan, [name], who maintains a database of all state-trained peer specialists. [name] served on the expert panel that developed the PREVAIL intervention, assisted with hiring during the R34, and will continue to support the project throughout the R01 (see Letter of Support). [name] will facilitate recruitment of peer specialists for the study via direct personal contacts and e-mail announcements to peer specialists who reside in or near Washtenaw and Oakland Counties. In order to allow participants the opportunity to choose from among several PREVAIL peer mentors, we will hire 6 to 8 peer providers with diverse backgrounds to deliver the intervention on a part-time hourly basis. We do not anticipate difficulty hiring peer providers based on our experience during the R34 and with other peer support research trials.

Concomitant Treatment

Contamination of the EUC group would most likely occur via receipt of non-study sources of peer support. We will exclude participants who are currently receiving or intending to receive either individual peer mentorship from a Certified Peer Support Specialist, or group-based, suicide prevention-focused peer support, on a biweekly or more frequent basis outside of the study, and will measure non-study peer support via the adapted Health Services Inventory measure. (87) Indirect contamination could occur via communication between PREVAIL and EUC participants while on the inpatient unit, though any such occurrences are expected to be of minor significance relative to the subsequent greater dose of peer mentorship received by PREVAIL participants.

Allowed Interventions

Once a participant is enrolled into the study, there is no restriction on the types of other care they may receive during their participation. If a participant is assigned to the peer mentorship intervention arm, study staff will send a letter to the participant's outpatient mental health provider informing them that the patient will be receiving peer mentorship as part of this study.

Prohibited Interventions

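### Exclusion 4 does not exclude patients already mentored one-to-one by a peer recovery coach, although coaches are one of the two provider types that deliver PREVAIL

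*Combined protocol and SAP*

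**What the plan says.** Exclusion Criteria, item 4, removes patients who are "already receiving or intending to receive individual peer mentorship from a Certified Peer Support Specialist". A second limb covers peer groups aimed at preventing suicide, and both limbs apply only when contact is at least biweekly. The provider restriction applies to the individual mentorship. The group limb names no provider type.

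Concomitant Treatment (under STUDY INTERVENTIONS) gives the reason for the exclusion: "Contamination of the EUC group would most likely occur via receipt of non-study sources of peer support". It then restates the exclusion with the same single credential, and adds that non-study peer support will be measured with the adapted Health Services Inventory.

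Delivery and Duration says the intervention is delivered by "peers specialists or peer recovery coaches - trained and certified by the State of Michigan" and that "both types of peer providers utilize their lived experience with recovery to support others". The pilot description of mentor training likewise defines a peer mentor as either provider type once trained in PREVAIL. The Background, on implementation of peer support, presents recovery coaches as a separately trained and separately reimbursed group "who serve similar populations in community mental health programs".

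No other exclusion covers individual mentorship by a coach. Allowed Interventions and Prohibited Interventions place no limit on other care after enrolment.

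**The concern.** The protocol identifies a contamination route and assigns an exclusion to control it, but defines that exclusion by one of the two credentials it uses for its own mentors. Read literally, a patient who sees a peer specialist every two weeks is excluded and a patient who sees a recovery coach every week is not. No reason is given for the difference.

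If coached patients are enrolled and allocated to EUC, some controls receive continuing one-to-one peer support during follow-up. To the extent that this support works as PREVAIL is meant to, the difference between arms shrinks on both primary outcomes and on the hope and belongingness measures.

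The exposure need not be small in contact count. Taking biweekly as every two weeks, the threshold is 12 / 2 = 6 contacts over 12 weeks. That equals the 6 encounters that define the per-protocol cohort and slightly exceeds the pilot mean of 5.6.

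**Working it through.** **Inputs.** From Sample Size in the SAP: attempt rates at 6 months of 36% (control) and 22% (intervention), 490 enrolled, 25% dropout, 184 analysable per group, two-sided 0.05, stated power 84%. Assumed, because the documents give neither: q, the share of controls with a qualifying outside coach, and f, the fraction of the PREVAIL effect that such a coach delivers.

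**Formula.** Two-proportion normal approximation with n per arm, control rate pC, intervention rate pI, and p̄ = (pC + pI)/2:

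- SE0 = √[2 p̄(1 − p̄)/n]
- SE1 = √[(pC(1 − pC) + pI(1 − pI))/n]
- Power = Φ[(pC − pI − 1.96·SE0)/SE1]

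**Reproducing the plan.** 490 × 0.75 = 367.5, taken as 368, or 184 per arm. With p̄ = 0.29:

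- SE0 = √(2 × 0.29 × 0.71/184) = 0.0473
- SE1 = √((0.36 × 0.64 + 0.22 × 0.78)/184) = 0.0467
- Power = Φ[(0.14 − 1.96 × 0.0473)/0.0467] = 84.4%

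This agrees with the stated 84%.

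**Dilution.** Hold the intervention arm at 22% and set pC = 0.36 − q × f × 0.14. This assumes that outside coaching adds nothing for a participant who also has PREVAIL.

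| q | f | Control rate | Difference | Power |
|---|---|---|---|---|
| 0 | – | 36.00% | 14.00 points | 84.4% |
| 2% | 1 | 35.72% | 13.72 | 83.0% |
| 5% | 1 | 35.30% | 13.30 | 80.8% |
| 10% | 1 | 34.60% | 12.60 | 76.7% |
| 2% | 0.5 | 35.86% | 13.86 | 83.7% |
| 5% | 0.5 | 35.65% | 13.65 | 82.7% |
| 10% | 0.5 | 35.30% | 13.30 | 80.8% |

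Only the product q × f matters. Power drops below 80% once it exceeds about 6%.

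**Accrual if coached patients are excluded.** The Enrollment section expects 480 + 720 = 1,200 candidates a year, of whom 60% are ineligible and 22% refuse. That leaves 18%, or 216 a year, and 648 over 3 years. Losing an assumed 10% leaves 648 × 0.90 = 583, still above 490.

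**The case against.** The strongest reply is that an outside coach is not PREVAIL. A peer mentor in this trial has PREVAIL training. The Background says that neither credential's standard training addresses suicide, and it ties recovery coaches' lived experience to substance use. The rationale for the EUC condition even warns that a peer specialist without PREVAIL training may give harmful messages, so dilution toward the null is itself an assumption. This stands. It makes f = 1 an upper bound and leaves the direction unproven.

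Second, the narrow wording may be intended. Criterion 4 also admits less frequent mentorship and groups not focused on suicide, and the inclusion rationale seeks a broadly representative sample. That is possible, but no such reason is stated, and the protocol otherwise treats the two provider types alike.

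Third, coached patients enter both arms. Randomisation balances who has a coach, but the contrast for those patients becomes PREVAIL plus coach against coach. If coaching added equally in both arms there would be no dilution, so the table depends on the stated assumption that it does not.

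Fourth, non-study peer support is measured. This is a real mitigation. However, the item wording is not in the documents, and nothing in the Data Analysis section uses the measure to examine contamination.

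A reader might infer more than the text supports, in three ways:

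- **That sites must enrol coached patients.** The criteria only fail to exclude them.
- **That the trial is seriously underpowered.** At q = 20% and f = 1 power would be about 67%, but this needs one control in five to have a coach as effective as PREVAIL. Nothing in the documents supports that.
- **That coaches can be hired without meeting the mentor requirements**, because "Peer specialists will also be required to be in stable recovery". The preceding sentence covers certified peer providers generally, and the protocol elsewhere uses *peer specialist* loosely for any mentor, as in the postvention and study-phone provisions. This is at most a terminology clean-up.

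**Conclusion.** The mismatch in wording is certain and occurs in both places where the exclusion is stated. As written, the criterion does not cover one of the two provider types that the trial treats as suitable to deliver the intervention, so it only partly performs the contamination control assigned to it.

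The consequence is uncertain. Under the dilution model the cost is 1 to 2 points of power if few controls have a coach (q = 2% at either f, or q = 5% at f = 0.5). It reaches about 8 points (84.4% to 76.7%) at q = 10% with full PREVAIL-equivalent benefit. Both q and f are assumptions, as is the absence of added benefit in the PREVAIL arm. The point should be addressed because the correction is cheap and specific. The documents do not show that a material bias exists.

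**What to change.** **Wording.** In Exclusion Criteria item 4 and in Concomitant Treatment, replace the single credential with *from a certified peer provider (peer support specialist or peer recovery coach)* and keep the frequency threshold. If the narrower wording was intended, state the reason in both places.

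**Participants already enrolled.** This part applies even if recruitment has closed.

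- Confirm that the Health Services Inventory item captures recovery-coach contact and its frequency. The protocol describes the inventory as covering lifetime or 3-month intervals, so check that the baseline version identifies current contact.
- Report coach contact by arm at baseline, 3 and 6 months.
- Pre-specify a sensitivity analysis of both primary outcomes that excludes participants with coach mentorship at or above the threshold at baseline. Because this selects on a pre-randomisation variable, it keeps the randomised comparison. Contact that starts after randomisation should be described, not used to exclude.

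**Cost.** A short amendment, one more phrase in the screening question, and one extra analysis. Some eligible patients are lost, along with some generalisability to suicidal patients with substance use who have a coach. The change reduces contamination but does not remove it, because care after enrolment remains unrestricted.
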